2.1 Efficacy Endpoints

2.1.1 Primary Efficacy Endpoint

The primary efficacy endpoint is linear healing rate (LHR) from TV1 to EOT as compared with LHR from RV1 to TV1. LHR will be calculated by linear regression of the 4 measurements in each phase, with linear wound edge advance being based on the change with respect to time of wound area divided by perimeter, according to Vidal's method (22) [Each participant will be used as his/her own control, i.e. a participant's healing trajectory before introduction of treatment will be compared to his/her healing trajectory after introduction of treatment. Wound area and perimeter will be measured by a blinded independent wound expert using digital images taken at baseline (RV1), first treatment visit (TV1) and at EOT.

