3.1 Study Population

3.1.1 Number of Participants

A total of 60 patients will be randomised into the study

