4.2.2 Treatment Visit 1 (TV1) – Randomisation and Post-randomisation

Perform the activities below in the following order:

- Randomise the participant. At the randomisation visit, the study ulcer needs to be ≥ 2 cm² and ≤ 30 cm². If other ulcerations are present on the same leg, they need to be at least 2cm away from the study ulcer
- Apply SC.
- Apply appropriate gekoTM to those participants randomised to either gekoTM group.
- Assess for any post-application AE.
- Provide the participant with gekoTM devices as applicable in accordance with the randomisation outcome
- Schedule the next study visit in one week's time.

NB. Each gekoTM device can only be used twice.

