10.5.2 Results of Interim Analysis

The new sample size calculation is:

Based on a pair-wise comparison of geko™ 12h run-in vs treatment:

From the interim data, there is a mean difference of 0.58 mm/week between run-in and treatment and a standard deviation of 0.97 mm/week.

Assuming requirements of 80% power and $p=0.05$ (2-sided) 25 subjects would be needed in the geko™ 12H group. (30)

Little benefit is foreseen in continuing the geko™ 6h group, as statistical significance is not expected at the projected number of subjects in this trial.

From the results of the Interim Analysis the new Treatment Groups are:

Group	Description
SC	Standard care (multilayer, multicomponent compression intended for the treatment of VLU)
geko 12h	geko™ version XW, W-3 or variant (12 h daily neuro-stimulation) and SC

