10.12 Analysis Methods

A SAP will be developed and approved before the database is locked. The SAP will present the detailed statistical methodology to be used in analysing the efficacy and safety data from this study.

All statistical tests will be two-sided and a 0.05% significance level maintained throughout the analyses.

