10.12.1 Efficacy Analyses

Primary Endpoint: The primary efficacy endpoint is linear healing rate (LHR) from TV1 to EOT as compared with LHR from RV1 to TV1. LHRs will be measured by a blinded wound expert using digital images at RV1, TV1, and EOT.

Within treatment groups, treatment phase will be compared to run-in phase by paired non-parametric test (Wilcoxon signed rank). Effects will be compared between groups using non-paired non-parametric tests (Mann-Whitney).

Secondary Endpoints:

Weekly LHR shall be compared as above.

EOT healing status between groups shall be compared by Mann-Whitney U test on the PWAT scores. Weekly LHR can be tested using the same method (and same wording) as final LHR. Incidence of healing shall be compared between groups using Fisher's exact test.

Intra-group pain reduction measured on a visual analogue scale (VAS) will be analysed using paired t-test.

Inter group differences in time to clinically significant reduction in VAS shall be tested using Mann-Whitney u-test.

Intra-group changes to both Quality of Life (QoL) instruments in the study (CWIS and EQ-5D-5L) shall be tested using Wilcoxon signed rank test.

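### Healing is compared by an unadjusted Fisher's exact test although TV1 ulcer area, read blind from a pre-randomisation image, is available as a prognostic covariate; the power lost is modest

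*Combined protocol and SAP*

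**What the plan says.** - **Test.** Section 10.12.1: "Incidence of healing shall be compared between groups using" Fisher's exact test. No covariate or stratum is named. ANCOVA occurs only in the abbreviation list.
- **Endpoint.** Healing is the judgement of the principal investigator or a designee that the ulcer is fully re-epithelialised and dry, confirmed at least 7 days later (sections 2.1.2 and 9.9.8). Participants who withdraw or do not heal in the Treatment Phase count as failures (section 10.11). That phase lasts four weeks (Synopsis).
- **Area at randomisation.** Section 4.2.2: "the study ulcer needs to be ≥ 2 cm² and ≤ 30 cm²".
- **How area is obtained.** Section 2.1.1: "Wound area and perimeter will be measured by a blinded independent wound expert using digital images taken at baseline (RV1), first treatment visit (TV1"), and again at EOT. Section 4.2.1 places the TV1 image before randomisation. Section 9.9.9 sends all images to the expert at the end of the study, and section 10.4 removes participant and visit data from them.
- **Size.** Section 3.1.1: "A total of 60 patients will be randomised into the study". The arm ratio is not given.
- **Allocation.** Section 10.3 uses adaptive covariate randomisation and names no covariate.
- **Detail.** Sections 10.1 and 10.12 leave detailed methods to a separate SAP.

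**The concern.** A small ulcer can close in four weeks at an edge advance that would leave a large one open. TV1 area is therefore an obvious prognostic variable for healing, and it is already collected under blinding. A test that ignores it leaves the variation due to area in the error term, which costs power. The protocol accepts this reasoning for LHR: section 10.7.1 expects participants to be heterogeneous and normalises each to the run-in rate. Healing gets no comparable treatment.

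This comparison is also the only between-arm test of closure in section 10.12.1. Closure reported by participants during follow-up is listed as an endpoint in section 2.1.3 but has no test.

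**Working it through.** **1. The plan's own figure.** No power, healing rate or sample size is stated for healing. The only calculation is for the paired LHR comparison in section 10.5.2, where "there is a mean difference of 0.58 mm/week between run-in and treatment and a standard deviation of 0.97 mm/week", giving "25 subjects would be needed in the geko™ 12H group" at 80% power and two-sided 0.05.

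- Normal approximation: ((1.960 + 0.842) × 0.97 / 0.58)² = 21.95, so 22.
- Exact noncentral t: 24 (power 0.801; 0.818 at 25).
- Dividing 24 by 0.955 for the Wilcoxon test: 25.1.

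The stated 25 is reproduced to within one participant by the t calculation. It says nothing about healing.

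**2. Geometry of closure.** For a circle, radius = √(area/π). Edge advance needed per week is radius/4. On the area-over-perimeter scale of section 2.1.1, area/perimeter = radius/2, so the need is radius/8.

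| TV1 area | Radius | Edge advance needed | Area/perimeter scale |
|---|---|---|---|
| 2 cm² | 8.0 mm | 2.0 mm/week | 1.0 mm/week |
| 10 cm² | 17.8 mm | 4.5 mm/week | 2.2 mm/week |
| 30 cm² | 30.9 mm | 7.7 mm/week | 3.9 mm/week |

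The range is √(30/2) = 3.9-fold. The SD in section 10.5.2 is 0.97 mm/week.

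**3. Anchor for the healing rate.** Section 1.3 cites about 45% healed at 12 weeks on compression. With a constant hazard (assumption), the 4-week figure is 1 − 0.55^(4/12) = 18%.

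**4. Power by simulation.** Assumptions:

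- 30 per arm and two-sided 0.05;
- TV1 area log-uniform on 2 to 30 cm², circular ulcers;
- LHR normal with SD 0.97 mm/week on the area/perimeter scale;
- an ulcer heals if four weeks of LHR cover its need.

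The adjusted test is a score test. It fits a logistic regression of healing on log area without treatment, takes residuals e = y − p̂, forms U = Σ(t − ½)e, and refers U²/V to chi-square on 1 df, with V the randomisation variance of U.

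| LHR shift | Healed, SC vs geko | Fisher | Unadjusted chi-square | Area-adjusted | Gain from area |
|---|---|---|---|---|---|
| 0.58 | 10% vs 21% | 12% | 24% | 25% | 1 |
| 0.58 | 19% vs 35% | 18% | 26% | 31% | 5 |
| 0.58 | 32% vs 50% | 20% | 27% | 35% | 8 |
| 0.58, 10% dropout as failure | 9% vs 19% | 10% | 21% | 22% | 1 |
| 0.58, 10% dropout as failure | 18% vs 31% | 16% | 23% | 27% | 4 |
| 1.16 | 19% vs 53% | 69% | 78% | 87% | 9 |

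Near the 18% anchor, the gap from Fisher to the adjusted test is 31 − 18 = 13 points: 26 − 18 = 8 from Fisher's conservatism and 31 − 26 = 5 from area. Type I error of the adjusted test was at most about 0.054. Fisher's was 0.01 to 0.03 at null healing rates of 10 to 33%.

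With 0 to 20% dropout counted as failure, the gain from area is about 1 to 5 points at a shift of 0.58 and 6 to 10 points at 1.16. The 8-point row needs SC healing of about a third and no dropout. When SC healing is below about 7%, the gain at 0.58 is about nil.

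**5. Scale and level.** If LHR is read as direct edge advance, SC healing falls below about 6% and no test has useful power at 0.58. Section 10.12 prints "All statistical tests will be two-sided and a 0.05% significance level maintained throughout the analyses". It is read here as 0.05, as in the sample-size text. Applied literally, it would cut Fisher's power for 20% vs 40% from 30% to 2%.

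**The case against.** Fisher's test is valid, healing is secondary, and the primary LHR analysis already uses each participant as own control. Detailed methods are deferred to a SAP. Healing is a clinical judgement that includes drainage and durability, and withdrawals count as failures; all three loosen the link with area. With 20% dropout as failure and SC healing of 10 to 18% before dropout, checks over several area distributions put the gain at −1 to +3 points. All of this stands, and it limits the size of the point. The deferral does not remove it, because section 10.12.1 already fixes Fisher's test and nothing signals an adjusted analysis.

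A reader might infer more than the documents support:

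- **That area explains most of who heals.** No association is reported. In simulations with assumed healing rates the correlation of healing with log area was −0.32 to −0.50, a linear R² of 0.10 to 0.25. That is strongly prognostic, but it is not most of the variation.
- **That area is measured before randomisation.** Only the image is; the blinded reading comes at the end of the study. Validity as a baseline covariate is unaffected.
- **That omitting area costs 13 to 22 points.** Gaps of that size appear against Fisher under large assumed effects such as 19% vs 48%, and 10 to 11 points of each gap are Fisher's conservatism.
- **That the arms will be imbalanced on area.** The allocation covariates are unnamed, so area may or may not be among them.

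**Conclusion.** The point holds as a modest loss of efficiency on a secondary endpoint. TV1 area is a valid, strongly prognostic covariate that is already collected, and the planned test ignores it. With about 30 per arm, adjustment adds roughly 1 to 5 points of power at the interim shift and about 6 to 10 points at twice that shift; replacing Fisher's conservatism accounts for a further 7 to 12 points. Adjustment does not rescue the endpoint: at the interim shift adjusted power is still only about 22 to 32%.

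These figures rest on assumed 1:1 allocation, circular ulcers, log-uniform areas, the area/perimeter reading of LHR and assumed SC healing rates. The direction is secure except where healing is rare, when there is little to gain by any test. The change is worth making because it costs almost nothing before database lock and would be post hoc afterwards.

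**What to change.** In section 10.12.1, and in the SAP before database lock, replace the sentence on healing with wording such as:

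> Incidence of healing will be compared between groups with adjustment for log TV1 ulcer area (blinded reading) and for every covariate used in the adaptive allocation, by a covariate-adjusted score test. The effect estimate is the standardised risk difference with 95% CI. The unadjusted 2x2 table with Fisher's exact test is supportive.

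Three details need settling at the same time:

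- Name the allocation covariates.
- Say how the model is fitted if events are few, for example by Firth penalisation.
- If a re-randomisation p-value is used, re-run the actual allocation algorithm, including the change from three arms to two. Freely permuting the labels is not a re-randomisation test under covariate-adaptive allocation.

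The cost is a few lines of text and code, with no new data. The adjusted result is slightly harder to explain than a 2x2 table, which is why the table stays.

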
Secondary Efficacy
 
The overall secondary efficacy endpoints are:
 
 • Weekly LHR of the study ulcer measured by an independent blinded wound expert using digital images taken at each weekly visit until EOT. • Wound healing status at baseline and EOT assessed by an independent blinded wound expert using the Photographic Wound assessment Tool (PWAT) to evaluate digital images taken at RV1, TV1 and EOT and at HCV, if scheduled. • Incidence of healing at EOT, as determined by the by the PI or designee. 
The participant reported secondary efficacy endpoints are:
 
 • Time from TV1 to clinically significant pain reduction measured using a Visual Analogue Scale (VAS) instrument. For the purpose of this protocol a clinically significant reduction of pain is a mean reduction of ≥ 20.65 mm or a mean decrease of $\geq 10-20\%$ in pain as measured on a 0-100 mm VAS. • Time from TV1 to first instance of no study ulcer pain measured using VAS. (No pain = < 5mm on VAS when VAS scores: 0-4 mm = no pain; 5-44 mm = mild pain; 45-74 mm = moderate pain; and 75-100 mm = severe pain) (1). • Pain score at EOT measured using VAS • Change from TV1 in Quality of Life (QoL) at EOT, assessed using the Cardiff Wound Impact Schedule (CWIS) • Change from TV1 in QoL at EOT, assessed using EQ-5D-5L 
 • Wound closure as reported by participants during the Follow-up Phase (FP1-FP3) 	

Safety Assessments
 
Safety will be assessed using the following parameters:
 
 • Incidence of AEs • Incidence of SAEs • Incidence of study ulcer infection • Incidence of study treatment related AEs (including geko™, compression bandaging and any dressings used to treat the study wound) • Incidence of investigational device (geko™) related AEs • Pain in the ulcer site (sudden onset of pain or increase in pain during the study Treatment Phase) 	

Trial Design: This study is designed as a prospective, multicentre, randomised, assessor blinded study designed to compare the efficacy, including participant reported outcomes, of a geko™ treatment in
	

Name of Sponsor/Company: Firstkind Ltd, [name]	
Name of Study Product: geko™ neuromuscular stimulator	

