1.6 Study Rationale, Benefits and Risks

This study is designed to evaluate the efficacy of two geko™ daily treatment durations in conjunction with Standard Care (SC), consisting of multilayer, multicomponent compression therapy intended for the treatment of VLU, compared with each other and to that of SC alone in participants with VLUs. geko™ has been shown to facilitate wound healing in earlier studies (See Section 1.5 Summary of prior clinical studies) and patients receiving the geko™ 6h or 12h daily in addition to SC may experience faster wound healing as well as greater pain reduction than patients treated with SC alone. We believe that treatment with geko™ will in conjunction with SC potentially lead to faster healing and re-epithelialisation than treatment with SC alone for patients with VLU.

A potential risk for participants randomised to the geko™ daily treatments is the possibility of eczema at the application site. This, however, is unlikely based on previous experience with geko™ (20). Potential adverse events for all research participants in this study are intrinsic to the nature of VLUs, including but not limited to: pain and infection at the wound site, and maceration of the surrounding skin.

Not all patients may respond to the geko™ stimulus. Therefore, patients with no involuntary movement of the lower leg/foot at the maximum tolerable device setting will be excluded from the study.

2 Study Objective

The objective of this study is to compare the efficacy of a daily geko™ device treatment durations of 12 hours, in conjunction with SC, to SC alone, in patients with venous leg ulcers.

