9.4 Quality of Life Assessment Questionnaire (CWIS and EQ-5D-5L)

The Cardiff Wound Impact Schedule, CWIS, will be used to assess the "disease specific" QoL. A generic QoL questionnaire, the EQ-5D-5L questionnaire, will be used to assess the effects of treatments on the participants' QoL. Results may be used to derive a patient-reported outcome useful for health-related QoL claims on the investigational device treatment.

The questionnaires (and instructions for completing them) will be provided to all participants at the first Run-in Phase visit (RV1) and at TV1 prior to the application of randomised treatment. The questionnaires will also be provided and collected upon EOT, as part of the End of Study procedures.

The QoL assessments will be performed prior to any other study procedures, when scheduled, to minimise bias.

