10.7.3 Participant reported secondary efficacy endpoints

Participant reported secondary efficacy endpoints are:

- Time from TV1 to clinically significant pain reduction measured using a Visual Analogue Scale (VAS) instrument. For the purpose of this protocol a clinically significant reduction of pain is a mean reduction of ≥ 20.65 mm or a mean decrease of $\geq 10-20\%$ in pain as measured on a 0-100 mm VAS (23; 24).
- Time from TV1 to first instance of no study ulcer pain measured using VAS.

(No pain = < 5 mm on VAS when VAS scores: 0-4 mm = no pain; 5-44 mm = mild pain; 45-74 mm = moderate pain; and 75-100 mm = severe pain) (1).

- Pain score at EOT measured using VAS.
- Change from TV1 in QoL at EOT assessed using the CWIS.
- Change from TV1 in QoL at EOT assessed using EQ-5D-5L.

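### Section 10.12.1 names only within-arm tests for VAS pain reduction, CWIS and EQ-5D-5L although the trial compares arms, and the pain-response definition behind its one between-arm participant-reported test has no single participant-level reading

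*Combined protocol and SAP*

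**What the plan says.** The Study Objective (Section 2) is to compare geko "in conjunction with SC, to SC alone, in patients with venous leg ulcers". The Trial Design paragraph of the Synopsis describes a study "designed to compare the efficacy, including participant reported outcomes", and Section 3 says the same. Section 9.4 adds: "Results may be used to derive a patient-reported outcome useful for health-related QoL claims on the investigational device treatment".

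For the participant-reported outcomes, Section 10.12.1 names three tests:
- VAS pain: "Intra-group pain reduction measured on a visual analogue scale (VAS) will be analysed using paired t-test".
- CWIS and EQ-5D-5L: "Intra-group changes to both Quality of Life (QoL) instruments in the study (CWIS and EQ-5D-5L) shall be tested using Wilcoxon signed rank test".
- Time to pain response: "Inter group differences in time to clinically significant reduction in VAS shall be tested using Mann-Whitney u-test".

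The general sentence on comparing effects between groups by Mann-Whitney stands under the primary endpoint, and only weekly LHR is linked back to it. PWAT scores and incidence of healing have their own between-group tests.

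Pain response is defined in the Synopsis, Section 2.1.3 and Section 10.7.3: "For the purpose of this protocol a clinically significant reduction of pain is a mean reduction of" at least 20.65 mm, or a mean decrease of at least 10-20%, on a 0-100 mm VAS. The listed pain-level endpoint is the VAS score at EOT. The QoL endpoints are changes from TV1 to EOT.

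Sections 10.1 and 10.12 defer detailed methodology to a separate SAP, to be approved before database lock.

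**The concern.** The SC arm is there to show what happens to pain and quality of life under compression and the passage of time. A signed rank or paired t-test inside the geko arm asks only whether participants changed. It can be significant with no device effect at all, and placing it beside the same test in the SC arm does not compare the two changes. With the tests as named, the QoL and pain-change results would not answer the trial's question, although Section 9.4 foresees that QoL results may support claims for the device.

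That leaves time to pain response as the only named between-arm test of a participant-reported outcome. Its event needs a rule that says, for one participant at one visit, whether a response has occurred. The definition is worded as a mean, gives a range as its percentage threshold, and does not say what the percentage is a percentage of. Who responds, and when, depends on how the analyst reads it.

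**Working it through.** **1. The plan's own figure.** Section 10.5.2 gives a mean difference of 0.58 and an SD of 0.97 mm/week, so d = 0.58/0.97 = 0.598. By the exact paired t, 24 participants give 80.1% power and 25 give 81.8%, which agrees closely with the stated 25. That figure sizes a within-arm LHR comparison. The documents give no target difference or SD for VAS, CWIS or EQ-5D-5L, so what follows is in SD units of change.

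**2. Contrasting two within-arm tests.** Assumptions: 60 randomised (Section 3.1.1) split equally, so n = 30 per arm; normally distributed changes with the same true mean d (in SDs) in both arms; two-sided alpha 0.05 as in Section 10.5.2 (Section 10.12 prints 0.05%). If p is the power of the within-arm test, then P(geko significant, SC not) = p(1 - p), which cannot exceed 25%. For the paired t, p comes from the noncentral t with 29 degrees of freedom and noncentrality d√30. At d = 0.4 the noncentrality is 2.19, p = 0.563, and 0.563 × 0.437 = 0.246. The Wilcoxon column is from 20,000 simulated trials.

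| d | p (paired t) | p(1 - p) | Wilcoxon, simulated |
|---|---|---|---|
| 0.1 | 0.083 | 0.076 | 0.075 |
| 0.2 | 0.185 | 0.151 | 0.144 |
| 0.3 | 0.355 | 0.229 | 0.222 |
| 0.4 | 0.563 | 0.246 | 0.246 |
| 0.5 | 0.754 | 0.186 | 0.195 |
| 0.6 | 0.888 | 0.099 | 0.110 |
| 0.7 | 0.959 | 0.039 | 0.043 |
| 0.8 | 0.988 | 0.011 | 0.015 |

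A between-arm Mann-Whitney on the same simulated changes rejects in 4.7% to 5.2%, whatever d is. That rate counts both directions, so about half of it would favour geko. At 24 per arm (30 less the 20% discontinuation in Section 10.2) the Wilcoxon pattern runs from 4% to 25%.

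**3. The pain definition.** A TV1 score is at most 100 mm, so 20% of TV1, or of the scale, is at most 20 mm. A fall of 20.65 mm is therefore always at least 20.65% of TV1 and more than 20% of the scale. Because the two limbs are joined by *or*, the millimetre limb never decides a case. For a TV1 score of 30 mm the required fall is:
- 10% of TV1: 0.10 × 30 = 3 mm
- 20% of TV1: 0.20 × 30 = 6 mm
- 10% of the scale: 10 mm
- 20% of the scale: 20 mm

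**4. What a between-arm test can detect.** For a two-sample t-test at 80% power and two-sided 0.05, the detectable difference is 0.74 SD at 30 per arm, 0.83 SD at 24 and 0.91 SD at 20.

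**The case against.** The strongest reply is that detailed methodology is left to an SAP that is not among the documents, and that Section 10.12.1 does not call the within-arm tests the only ones. A reader might infer that the trial will have no between-arm analysis of QoL or pain. The documents do not support that, and the point is limited to what the protocol names. Deferral still does not cure it. Section 10.1 says Section 10 itself gives the tests to be performed, and for these outcomes it does name tests. The choice is not loose wording either, because neighbouring sentences distinguish within-group from between-group tests. Section 16 also bars sites and investigators from publishing analyses not specified in the protocol.

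A reader might also take 25% as the false-positive rate of this plan. It is not. The pattern misleads only if someone contrasts the two within-arm results; nothing says the sponsor will do so, and Section 9.4 says only that results may be used for claims. These are secondary endpoints.

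Nor does the text support saying that the pain definition cannot be applied to a participant. Once the word *mean* is dropped it can be applied, in several ways. The defect is that no single way is stated.

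Finally, 30 per arm may be too high. The 6-hour arm was dropped after the interim analysis, and the documents do not say whether its participants count toward the 60. This objection stands, and it is why the figure for 20 per arm is given.

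**Conclusion.** The concern holds in this form. For VAS pain reduction, CWIS and EQ-5D-5L the protocol names only tests that cannot answer its between-arm question, and its one between-arm participant-reported test has an event with no single participant-level meaning.

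The first part rests on the text alone. Its possible consequence, about 1% to 25%, is conditional on a contrast of within-arm results that the documents do not announce, on equal true change in both arms, on 30 per arm and on alpha 0.05. It exceeds the 5% of a direct test over most of the range examined, but not at changes of 0.7 to 0.8 SD. The second part is arithmetic on a 0-100 mm scale and needs no assumption. The change should be made before database lock; it does not touch the primary endpoint.

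**What to change.** (a) In Section 10.12.1, make a between-arm comparison the main analysis for:
- VAS pain at EOT, which is the listed endpoint, analysed as change from TV1 or with TV1 taken into account, and stated as such;
- change from TV1 to EOT in one pre-named CWIS score and one pre-named EQ-5D-5L score. Appendices 4 and 5 show several domains and scales in each, so leaving the score open leaves many tests.

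Mann-Whitney with a Hodges-Lehmann estimate and 95% CI would fit the plan's other rank tests. Use the ITT population of Section 10.10.1. Keep the within-arm tests as descriptive, treat these secondary results as supportive, and note that only the wound expert is blinded, so self-report may still carry expectation bias.

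(b) Before database lock, reconcile the Synopsis, Section 2.1.3 and Section 10.7.3 to one participant-level pain-response cut-off measured from TV1, with its denominator. The choice is the sponsor's. Apply it to the first visit at which it is met, so that a response seen before withdrawal or healing counts.

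**Cost.** Text only. VAS and both QoL instruments are already collected at TV1 before randomisation and at EOT, and final assessments are sought from those who withdraw. The drawback is low power: 80% only for differences of about 0.74 SD at 30 per arm, 0.83 SD at 24 and 0.91 SD at 20, so a null result would not exclude a smaller benefit. The protocol should also say whether participants from the dropped arm count toward the 60.
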